6.2. Screening Period

6.2.1. Screening Visit (Visit -1, Day -14 to -4)

If a screening hs-CRP result is outside inclusion criteria parameters, Screening may be extended up to 2 week to allow for retesting of an hs-CRP result that did not meet inclusion criteria. If laboratory test results are delayed, come back unable to perform analysis, come back indeterminate, or require confirmatory testing, the screening window may be extended until central laboratory results are available. Patients who have failed screening can be re-screened based on investigator's evaluation of the subject's eligibility and approval by the sponsor.

The following procedures will be performed at the Screening Visit (Week -1, Day -14 to -4):

- Obtain informed consent;
- Confirm inclusion/exclusion criteria;
- Record demographic information;
- Record medical history;
- Record prior/concomitant medications;
- Perform limited physical examination;
- Obtain vital signs prior to electrocardiogram (ECG) recording;
- Perform infectious disease screen;
- Perform serum pregnancy test for women of childbearing potential only;
- Perform FSH test for postmenopausal women only;
- Perform 12-lead ECG;
- Collect sample for chemistry and hematology assessments;
- Collect sample for urinalysis (including albumin);
- Collect sample for lipids and subfractions assessment;
- Perform spot urine protein-creatinine ratio assessment;
- Collect sample for screening IL-6 (central) assessment;
- Collect sample for hs-CRP assessment (may be repeated 1 time prior to Day 1. hs-CRP

values of 1.5 to <2 mg/L should be retested).

- Collect Ziltivekimab PK sample;
- Collect ADA sample; and
- Assess AEs

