6.3. Treatment Period (Visits 1 Through 9)

Following Screening, patients will return for visits and procedures within the study day windows specified below and in Appendix A.

For Visit 1, Visit 5 and Visit 7, all sample will be collected within 1 hour \pm 30 minutes prior to study drug administration. For other visits, all samples will be collected at approximately the same time (\pm 1 hour) as when the predose sample is collected on Day 1. Visits 2, 4, and 6 can be converted to phone visits, with the following procedures performed: Record prior/concomitant medications; Assess AEs. If there are any safety concerns raised during a phone visit, the patient may be asked to attend an unscheduled site visit.

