6.3.1. Visit 1 (Day 1)

The following procedures will be performed at Visit 1 (Day 1):

- Reaffirm inclusion/exclusion criteria;
- Update medical history;
- Record prior/concomitant medications;
- Obtain vital signs;
- Collect sample for chemistry and hematology assessments;
- Collect sample for urinalysis (including albumin);
- Collect sample for lipids and subfractions assessment;
- Collect sample for IL-6 (total) assessment (predose);
- Collect sample for hs-CRP assessment;
- Obtain BMI;
- Collect Ziltivekimab PK sample;
- Randomize patient;
- Collect ADA sample;
- Collect sample for fibrinogen, SAA, NT-pro-BNP, hemoglobin and albumin assessments;
- Collect sample for INR assessment (only for patients currently receiving warfarin);
- Assess AEs; and
- Administer assigned study drug (after all other Day 1 assessments).

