APPENDIX A: SCHEDULE OF PROCEDURES

	Screening: Days -14 Through -1 ^a	Treatment Period: Baseline Through Week 12									Safety Follow-Up: Weeks 12 Through 20	
Visit	-1	1	2 ^p	3	4 ^p	5	6 ^p	7	8	9/ET1	10	11/ET2
Week	-2		1	2	3	4	6	8	10	12/ET1	16	20/ET2
Day	-14 to -4	1	8+3 days	15+3 days	22+3 days	29+3 days	43+6 days	57+6 days	71+6 days	85+6 days	113+6 days	141+6 days
Informed consent ^b	X											
Inclusion/exclusion criteria	X	X ^c										
Demographic information	X											
Medical history/update	X	X										
Prior/concomitant medications	X	X	X	X	X	X	X	X	X	X	X	X
Limited physical examination ^d	X											X
Vital signs ^e	X	X		X	X	X		X		X	X	X
Infectious disease screen ^f	X ^g											
Serum pregnancy test ^h	X											X
FSH for postmenopausal women	X											
12-lead ECG ⁱ	X					X		X		X		X
Chemistry and hematology ⁿ	X ^g	X	X	X	X	X	X	X	X	X	X	X
Urinalysis (including albumin) ^j	X	X								X		
Lipids and subfractions (fasting 8 hours) ^{k,n}	X	X								X	X	
Spot urine protein-creatinine ratio ⁿ	X									X		
Screening IL-6 (central)	X											
IL-6 (Total) ⁿ		X ^l	X	X	X	X	X	X	X	X	X	X
hs-CRP ^{m,n}	X	X	X	X		X			X	X	X	X
BMI		X										
Ziltivekimab PK ⁿ	X	X	X	X	X	X	X	X		X	X	X

	Screening: Days -14 Through -1 ^a	Treatment Period: Baseline Through Week 12									Safety Follow-Up: Weeks 12 Through 20	
Visit	-1	1	2 ^p	3	4 ^p	5	6 ^p	7	8	9/ET1	10	11/ET2
Week	-2		1	2	3	4	6	8	10	12/ET1	16	20/ET2
Day	-14 to -4	1	8+3 days	15+3 days	22+3 days	29+3 days	43+6 days	57+6 days	71+6 days	85+6 days	113+6 days	141+6 days
Randomization		X										
Study drug administration (post-assessments)		X				X		X				
ADA ⁿ	X	X	X	X	X	X	X	X	X	X	X	X
Fibrinogen, serum amyloid A, NT-pro-BNP, hemoglobin and albumin ⁿ		X							X	X		
INR ^o		X	X	X	X	X	X	X	X	X		
Adverse events	X	X	X	X	X	X	X	X	X	X	X	X

ADA = anti-drug antibody; BMI = body mass index; ECG = electrocardiogram; ET1 = Early Termination for Treatment Period, ET2 = Early Termination for Safety Follow-up Period; FSH = follicle-stimulating hormone; HIV = human immunodeficiency virus; hs-CRP = high-sensitivity C-reactive protein; IL = interleukin; INR = international normalized ratio; lab = laboratory; PI = Principal Investigator; PK = pharmacokinetic(s).

^a Screening may be extended up to 1 week to allow for retesting of a hs-CRP result that did not meet inclusion criteria.

^b Signed informed consent must be obtained before any study-related procedures are performed.

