^o INR will be performed by the local lab only for patients currently receiving warfarin.

^p Visit 2, 4, and 6 can be converted to phone visits, with the following assessments performed: Prior/concomitant medications; assess adverse events.

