3.6.2 Clinical Laboratory Tests

Blood and urine samples for clinical laboratory tests will be collected and processed by a central laboratory.

Values and changes from baseline for lab parameters (excluding efficacy lab parameters) will be presented at each scheduled visit and baseline by laboratory test. The incidence of abnormalities (as defined by normal ranges) prior to the first dose of study drug and after the first dose of study drug will be summarized with counts and percentages of subjects.

All laboratory measurements will be listed.

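### For chemistry and hematology, the before/after-first-dose count of laboratory abnormalities compares 2 samples with 7 to 10, so it rises with no drug effect and does not isolate new abnormalities

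*SAP*

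**What the plan says.** For laboratory tests, SAP 3.6.2 plans values and changes from baseline at each scheduled visit, a listing of all measurements, and one further summary: "incidence of abnormalities (as defined by normal ranges) prior to the first dose of study drug and after the first dose". This is given as numbers and percentages of patients. The section does not say how many samples each period contributes, whether the pre-dose period means all earlier samples or only the Baseline value, or how a patient already out of range at baseline is treated.

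The sampling schedule is in the protocol. Section 6.2.1 (Screening) has "Collect sample for chemistry and hematology assessments". Section 6.3.1 repeats that sample on Day 1, before dosing, since drug comes last. In Appendix A the "Chemistry and hematology" row is marked at every visit from -1 to 11. Section 6.3 adds that "Visits 2, 4, and 6 can be converted to phone visits". A converted visit covers only medications and adverse events, so it yields no blood sample.

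For vital signs and ECG thresholds (SAP 3.6.3 and 3.6.4), the numerator is limited to subjects who were normal at baseline on that criterion and had at least one post-baseline outlier. The denominator is subjects with a baseline and at least one post-baseline assessment. Laboratory tests have no such rule.

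**The concern.** The natural reading of a count of subjects per period is the percentage with at least one out-of-range value in that period. Such a percentage grows with the number of samples taken. If one period has several times as many samples as the other, the two differ even when nothing about the patients has changed.

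The summary also does not link a patient's pre-dose status to the post-dose status. A patient out of range throughout counts in both columns, and one who becomes abnormal counts in the second only, but the two percentages do not separate these cases. In Stage 3 to 5 CKD many patients will enter with abnormal values, and in groups of 12 it matters to tell new abnormalities from old ones. Neutrophils and platelets, which Protocol 1.5 and 8.3 single out, and the liver enzymes belong to the panels with the largest imbalance.

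**Working it through.** The documents give no laboratory abnormality rate and no before/after ratio, so there is no planned figure to reproduce. The sample counts come from Protocol Appendix A and sections 6.2 to 6.4. The per-sample rate p and the within-patient correlation are assumptions, shown over a range.

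**Step 1. Count the scheduled samples.**

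| Panel | Before first dose | After first dose | After ÷ before |
|---|---|---|---|
| Chemistry, hematology | 2 (Visits -1, 1) | 10 (Visits 2–11); 7 if Visits 2, 4, 6 are by phone | 5.0; 3.5 |
| Urinalysis | 2 (Visits -1, 1) | 1 (Visit 9) | 0.5 |
| Lipids | 2 (Visits -1, 1) | 2 (Visits 9, 10) | 1.0 |
| Spot urine protein-creatinine ratio | 1 (Visit -1) | 1 (Visit 9) | 1.0 |

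**Step 2. Independent samples, no drug effect.** P(at least one abnormal in k samples) = 1 − (1 − p)^k. At p = 5%:
- k = 2: 1 − 0.95² = 9.75%
- k = 7: 1 − 0.95⁷ = 30.2%, ratio 3.1
- k = 10: 1 − 0.95¹⁰ = 40.1%, ratio 4.1

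**Step 3. Correlated values.** Take normal laboratory values with common within-patient correlation r, and a two-sided cutoff c with P(|Z| > c) = p. Then P(k) = 1 − E[{Φ((c − √r·z)/√(1 − r)) − Φ((−c − √r·z)/√(1 − r))}^k], averaged over standard normal z. At p = 5%:

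| r | 2 samples | 7 samples | 10 samples | Ratios |
|---|---|---|---|---|
| 0 | 9.75% | 30.2% | 40.1% | 3.1; 4.1 |
| 0.5 | 9.1% | 23.0% | 28.7% | 2.5; 3.2 |
| 0.8 | 7.8% | 14.9% | 17.3% | 1.9; 2.2 |

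For p from 2.5% to 10% and r from 0 to 0.8, the ratio runs from 1.8 to 4.5.

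Here r is the correlation of the laboratory values. The intraclass correlation (ICC) of the yes/no abnormality is a different scale: at p = 5%, r = 0.8 corresponds to a yes/no ICC of about 0.41. A beta-binomial calculation with yes/no ICC 0.5 gives 7.4% v 12.3% and 13.8%, ratios 1.7 and 1.9.

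**Step 4. Analytes that are usually abnormal.** With independent samples the ratio for both 7 and 10 post-dose samples is about 1.3 at p = 50%, 1.04 at 80% and 1.0 at 95%. Creatinine and eGFR in this population belong at this end.

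**Step 5. Other panels at p = 5%, independent samples.** Urinalysis: 5.0% after v 9.75% before, ratio 0.51. Lipids and spot urine protein-creatinine ratio: 1.0.

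**Step 6. The other reading of the pre-dose period.** If it means only the Baseline value (the last pre-dose one, SAP 3.1.3), the contrast is 1 v 7 to 10: 30.2/5.0 = 6.0 and 40.1/5.0 = 8.0 at p = 5%, independent samples.

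**Step 7. Between arms.** All arms share the schedule, so k is the same after dosing and the expected active-to-placebo ratio is 1.0 with no drug effect.

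**Step 8. The baseline-normal rule with no drug effect.** At p = 5% and independent samples, the expected treatment-emergent percentage is (1 − p) × [1 − (1 − p)^k]: 0.95 × 30.2% = 28.7% for k = 7 and 0.95 × 40.1% = 38.1% for k = 10. It still accumulates over samples, equally in every arm, so this table too must be read against placebo.

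**The case against.** The strongest reply is that this is one descriptive table in a 36-patient study. No test, primary result or stopping rule uses it. SAP 3.1.4 and 3.6 summarize by treatment group, so placebo appears alongside with the same schedule. Comparing post-dose percentages between arms is like for like. By-visit values and changes are planned, all measurements are listed, the neutrophil and platelet events of special interest have their own graded thresholds and summaries (SAP 2.3.4), and clinically significant worsening is reported as an adverse event. All of this stands, and it limits the consequence.

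It also rules out several stronger readings that a reader might infer:
- That every analyte will seem to worsen. Urinalysis goes the other way, and two panels are balanced.
- That inflation is a fixed 2- to 4-fold. The multiplier depends on an assumed rate and correlation and can be close to 1.
- That the table says nothing about the drug or hides neutrophil, platelet or liver-enzyme changes. The between-arm comparison is intact, and those analytes are summarized elsewhere.
- That phone visits bias the arms against each other. The option is open to all arms under blinding, and the documents identify no route to a difference.

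The SAP also does not say that conclusions will be drawn from after versus before. But the before/after split is the form it chose for this table, and the objection does not make that split interpretable or supply the missing link to baseline status.

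**Conclusion.** The point holds for chemistry and hematology. The before/after percentages rest on 2 v 7 to 10 samples and are not conditioned on baseline, so their contrast cannot be interpreted and does not isolate new abnormalities. With no drug effect the apparent rise is about 3.1- to 4.1-fold at 5% per independent sample, 1.9- to 2.2-fold at value correlation 0.8, and near 1 for persistently abnormal renal analytes. These sizes rest on assumed rates and correlations, and on reading the summary as at least one out-of-range value per subject per period; only the sample counts come from the documents. Urinalysis is biased downward, and lipids and spot urine protein-creatinine ratio are unaffected. The active-versus-placebo comparison is not biased by the schedule and the efficacy analysis is untouched. This is a cheap improvement to the safety reporting, not a threat to the trial's conclusions.

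**What to change.** In SAP 3.6.2, replace the before/after incidence with two summaries:
- (a) The proportion of patients out of range at each scheduled visit, by arm. Each patient then contributes one sample per visit.
- (b) Treatment-emergent abnormality by arm, under the rule in SAP 3.6.3 and 3.6.4. Numerator: in range at baseline and at least one post-baseline value out of range. Denominator: a baseline and at least one post-baseline assessment. Use all post-baseline samples, including Visits 2, 4 and 6 when taken, so that no on-treatment extreme is lost.

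State that both are to be interpreted as active versus placebo.

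The cost is SAP wording and one changed table shell, on data already scheduled for collection. SAP section 1 has the plan finalized before database lock, and the change should be made by then. There is one small downside: a patient already abnormal at baseline who worsens will appear only in the by-visit summaries and listings, unless a shift table by arm from baseline category to worst post-baseline category is added. That table sets one baseline value against the worst of many, so it too should be read only between arms.

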3.6.3 Vital Signs

Vital signs and change from Baseline in vital signs will be summarized descriptively at each visit by treatment group. The number and percentage of patients with exceeding pre-defined absolute and relative threshold values will be summarized. These threshold values are presented in Table 1.

When calculating the percentages for the criterion related to a threshold, the numerator will be the number of subjects with normal baseline with respect to the specific criterion and at least one post-baseline outlier value within the analysis period; and the denominator will be the number of subjects with a baseline and at least one post-baseline assessment within the analysis period.

Table 1 Pre-defined Threshold Value for Vital Signs

Parameter	Criteria
Systolic Blood Pressure (SBP)	>25% mmHg Increased or decreased from Baseline
SBP	>160 mmHg
Heart Rate (HR)	>100 beats per minute
Respiration Rate	>24 breaths per minute
BMI	>10% increased or decreased from Baseline

All vital signs measurements will be listed.

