3.1.4 Summary Statistics

All study-collected data will be summarized by treatment group for the appropriate analysis population using descriptive statistics, graphs, and/or raw data listings. Descriptive statistics for continuous variables will include number of patients (with non-missing values), mean, standard deviation (SD), median, first and third quartiles, minimum and maximum values for the observed value, and change from Baseline. Analysis of categorical variables will include frequency and percentage. The denominator used for the percentage calculation will be clearly defined.

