3.6 Safety Assessment

Safety data will be summarized by actual treatment received (and in total for selected analyses) based on the Safety population.

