The number and percentage of patients with TEAEs by occurrence time (0-2, 2-4, 4-6, 6-8, 8-10, 10-12 and >12 weeks) will also be summarized for each preferred term, system organ class, and treatment. The number of patients that completed each time period and the proportion of patients presenting TEAEs in proportion to the number of patients that completed the given time period will also be summarized.

Listings will be presented specifically for SAEs and TEAEs leading to discontinuation of study drug.

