3.6.4 Electrocardiograms

ECG interpretation (normal vs abnormal) will be summarized using frequency and percentage at each visit by treatment group. ECG intervals (ie, PR interval, QT interval, heart rate, and QTcF) will be summarized descriptively at each visit. The number and percentage of patients with exceeding pre-defined absolute and relative threshold values (PR interval >200 msec; QTcF >450 msec, >480 msec, and >500 msec; and QTcF increase from Baseline >30 msec and >60 msec) will be summarized. These threshold values are presented in Table 2.

When calculating the percentages for the criterion related to a threshold, the numerator will be the number of subjects with normal baseline with respect to the specific criterion and at least one post-baseline outlier value within the analysis period; and the denominator will be the number of subjects with a baseline and at least one post-baseline assessment within the analysis period.

Table 2 Pre-defined Threshold Value for ECG

PR interval	Criteria
-------------	----------

QTcF	>200 msec
QTcF	>450 msec
QTcF	>480 msec
QTcF	>500 msec
QTcF	Increase from Baseline >30 msec
QTcF	increase from Baseline >60 msec

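### New-outlier percentages for absolute vital-sign and ECG thresholds keep patients already abnormal at baseline in the denominator, and the supplementary interval TEAE proportion divides by interval completers

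*SAP*

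**What the plan says.** **Outlier percentages.** SAP 3.6.3 (vital signs) and 3.6.4 (ECG) use the same rule. On top, "the numerator will be the number of subjects with normal baseline with respect to the specific criterion" who also have at least one outlying value after baseline. Underneath, "the denominator will be the number of subjects with a baseline and at least one post-baseline assessment within the analysis period". The denominator carries no condition on baseline status. The ECG criteria are of two kinds: absolute limits ("PR interval >200 msec; QTcF >450 msec, >480 msec, and >500 msec") and changes ("QTcF increase from Baseline >30 msec and >60 msec"). SAP Table 1 mixes the two kinds in the same way for vital signs. Protocol 9.2.3.3 and 9.2.3.4 list thresholds but give no denominator.

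**TEAEs by time interval.** SAP 3.6.1 first plans a tabulation in 2-week bands to Week 12 and one band beyond: "The number and percentage of patients with TEAEs by occurrence time". It states no denominator there. It then adds the number of patients completing each band and "the proportion of patients presenting TEAEs in proportion to the number of patients that completed the given time period". What it means to complete a band is not defined; Protocol 4.7 defines completion only at Week 12 and Week 20.

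**General rules.** SAP 3.6: "Safety data will be summarized by actual treatment received (and in total for selected analyses) based on the Safety population". SAP 3.1.4: "The denominator used for the percentage calculation will be clearly defined". Neither changes the specific rules above.

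**The concern.** A table of new outliers is normally read as the risk among patients who could become outliers. Under the SAP rule, patients already past an absolute limit at baseline cannot be events but still lower the percentage. If the arms differ in how many such patients they contain, the table can show a difference that does not exist or hide one that does. With 12 patients per arm and randomization stratified only by CKD stage, balance in baseline PR or QTcF cannot be assumed.

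The interval TEAE figure has a different fault. Its numerator is not limited to completers, so someone who has a TEAE and then leaves the study within the band is counted above the line but not below it. The result is not a true proportion.

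Safety is the trial's secondary objective, and in arms this small one or two patients move every percentage.

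**Working it through.** The documents state no outlier rate or interval TEAE rate, so there is no figure of the plan's own to reproduce. The check applies the written definitions at the planned 12 patients per arm (SAP 2.2.4).

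**1. Which criteria can be diluted.** SAP Tables 1 and 2 hold 11 criteria.

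- Absolute (7): SBP >160 mmHg, heart rate >100, respiration rate >24, PR >200 msec, QTcF >450, >480 and >500 msec. A patient can already meet these at baseline.
- Change from baseline (4): SBP by >25%, BMI by >10%, QTcF increase >30 and >60 msec. Nobody meets these at baseline, so there is no dilution.

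Among the seven, Protocol 4.2 exclusion 14 removes patients with average screening SBP above 160 mmHg, with re-evaluation allowed. Baseline SBP above that limit should therefore be uncommon. The eligibility criteria set no PR or QTcF limit.

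**2. Size of the dilution.** Let x be new outliers and b the number abnormal at baseline among 12 patients, all with post-baseline data. b is an assumption; the documents do not give it.

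- Planned rate = x/12
- At-risk rate = x/(12 − b)
- Planned ÷ at-risk = (12 − b)/12

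With x = 2:

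| b | Planned | At risk | Factor |
|---|---|---|---|
| 0 | 2/12 = 16.7% | 2/12 = 16.7% | 1.000 |
| 1 | 16.7% | 2/11 = 18.2% | 0.917 |
| 2 | 16.7% | 2/10 = 20.0% | 0.833 |
| 3 | 16.7% | 2/9 = 22.2% | 0.750 |
| 4 | 16.7% | 2/8 = 25.0% | 0.667 |
| 5 | 16.7% | 2/7 = 28.6% | 0.583 |

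The factor is also the largest rate that can be reported: with b = 3, no more than 9/12 = 75%.

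**3. Effect on an arm comparison (assumed counts).**

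- A difference created: both arms have at-risk incidence 1/3. With b = 0 the report is 4/12 = 33.3%. With b = 6 there are 2 events among 6 at risk, and the report is 2/12 = 16.7%.
- A difference hidden: 4 of 12 at risk (b = 0, 33.3%) and 4 of 8 at risk (b = 4, 50.0%) are both reported as 4/12 = 33.3%.

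**4. Interval TEAEs.** Suppose 12 patients enter a band, D have a TEAE and leave during it, C complete it with a TEAE, and nobody else leaves. D and C are assumptions.

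- As written = (D + C)/(12 − D)
- On those entering the band = (D + C)/12

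| D | C | As written | Entering the band |
|---|---|---|---|
| 1 | 0 | 1/11 = 9.1% | 1/12 = 8.3% |
| 1 | 2 | 3/11 = 27.3% | 3/12 = 25.0% |
| 2 | 1 | 3/10 = 30.0% | 3/12 = 25.0% |
| 4 | 0 | 4/8 = 50.0% | 4/12 = 33.3% |

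The error is upward in each row. An extreme case shows that the ratio has no ceiling at 100%: D = 7, C = 0 gives 7/5 = 140%, against 7/12 = 58.3%. Patients who leave without a TEAE also drop out of the denominator, which again pushes the figure up.

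**The case against.** **The outlier rule is coherent.** Every patient in the numerator has a baseline and a post-baseline value, so the numerator is a subset of the denominator. The figure is the share of all assessed patients who developed a new outlier, and the SAP states its denominator openly. This stands: it is a legitimate quantity, but not the new-onset rate that restricting the numerator to normal-baseline patients suggests.

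**The reach is limited.** Four of the 11 criteria are immune, SBP >160 mmHg is largely screened out, and the true b could be zero. All of this stands. A reader might infer that vital-sign and ECG outlier rates are understated across the board; the documents do not support that.

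**The interval proportion is an extra.** It accompanies a number and percentage by occurrence time, which SAP 3.6 places on the Safety population, and the completer count is shown beside it. This stands.

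**Nothing is lost from view.** A reader might infer that an event leading to withdrawal disappears. SAP 3.6.1 does not remove leavers from the numerator. The event also stays in the main TEAE tables, and any TEAE leading to study drug discontinuation appears in the overview and its own listing. If a programmer matched the numerator to completers, this one figure would fall (D = 2, C = 1 gives 1/10 = 10.0% against 25.0%), but the SAP does not instruct that.

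**AE-related dropouts are not singled out.** The completer denominator removes anyone who leaves, for any reason. Protocol 4.5 asks patients who stop study drug to undergo early termination and safety follow-up procedures, so stopping drug need not mean failing to complete a band.

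**No decision depends on these tables.** They are descriptive, counts are given with the percentages, and the data are listed. This limits the severity but does not correct the tabulated rates.

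**Conclusion.** The point holds in limited form. Followed exactly, SAP 3.6.3 and 3.6.4 dilute the new-outlier rate for the seven absolute thresholds by the share of patients normal at baseline, and baseline imbalance can create or mask an arm difference. PR and QTcF are the likeliest places. With two new cases in an arm of 12, the gap runs from none (no patient abnormal at baseline) to 16.7% reported against 28.6% at risk (five abnormal). Where the trial falls in that range cannot be determined from the documents.

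The supplementary interval TEAE proportion in SAP 3.6.1 is not a true proportion and, as written, errs upward: by 0.8 percentage points (9.1% against 8.3%) for one leaver with a TEAE and no other case among 12. It does not conceal adverse events, and the main TEAE tables and listings are unaffected.

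The definitions themselves are clear on the page; only the size rests on assumed counts. Severity is minor to moderate.

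**What to change.** - **SAP 3.6.3 and 3.6.4, absolute thresholds:** define the denominator as patients who do not meet the criterion at baseline and have at least one post-baseline value in the analysis period. Leave the change-from-baseline criteria as they are.
- **SAP 3.6.1, interval TEAEs:** replace interval completers with patients under observation at the start of each interval, and say that patients off study drug but still in follow-up count as under observation.

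The cost is three SAP sentences and matching table footnotes, with no new data. Outlier denominators become slightly smaller and vary by row, so each row should show its own. The SAP is to be finalized before database lock, and the change belongs there.

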4.2. Exclusion Criteria

Patients who meet any of the following criteria will be excluded from participation in the study:

Laboratory values

1. Absolute neutrophil count $<2.0 \times 10^9$ /L during Screening;
2. Platelet count $<120 \times 10^9$ /L during Screening;
3. Spot urine protein-creatinine ratio >4000 mg/g (4.0 g/g) during Screening;
4. Alanine aminotransferase or aspartate aminotransferase $>2.5 \times$ upper limit of normal during Screening;
5. Positive testing for tuberculosis during Screening. Blood testing (eg, QuantiFERON) is

preferred, but a purified protein derivative (PPD) skin test read within 48 to 72 hours by a qualified healthcare professional may also be performed. If a patient is PPD positive but QuantiFERON negative, the patient is eligible;

6. Evidence of human immunodeficiency virus (HIV)-1 or HIV-2 infection by serology measured during Screening;
7. Hepatitis B or C by serology (eg, hepatitis B surface antigen or hepatitis C antibody positive) measured during Screening;

Medical conditions or diseases

8. Expected to require blood transfusion within 12 weeks post-randomization;
9. Thromboembolic event within 12 weeks prior to randomization;
10. Clinical evidence or suspicion of active infection;
11. History of peptic ulcer disease or gastrointestinal ulceration in the 12 months prior to randomization;
12. History of active diverticulitis in the 12 months prior to randomization;
13. History of inflammatory bowel disease that has been clinically active during the 12 months prior to randomization;
14. Uncontrolled hypertension (defined as an average systolic blood pressure >160 mmHg or an average diastolic blood pressure >100 mmHg) during Screening. Patients may be re-evaluated within 2 weeks, at the discretion of the Principal Investigator, for this criterion if antihypertensive therapy has been started or increased as a result of initial screening blood pressure being above these limits;
15. Planned coronary revascularization (percutaneous coronary intervention or coronary artery bypass grafting) or any other major surgical procedure during the time frame of the study;
16. Major cardiac surgical, non-cardiac surgical, or major endoscopic procedure within the past 6 months prior to randomization;
17. Prior gastric bypass surgery;
18. History of New York Heart Association Class IV congestive heart failure within 12 weeks prior to randomization;

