9.2.3.3. Vital signs

Vital signs and change from Baseline in vital signs will be summarized descriptively at each visit by treatment group. The number and percentage of patients with exceeding pre-defined absolute and relative threshold values (systolic blood pressure increase or decrease from Baseline >25% mmHg, >160 mmHg, or <90 mmHg; heart rate >100 beats per minute or <50 beats per minute; and respiration rate >24 breaths per minute) will be summarized.

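### The systolic blood pressure change threshold carries two units (percent and mmHg) wherever it appears, and the SAP counts rises and falls in one row

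*SAP*

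**What the plan says.** SAP section 3.6.3, Table 1, sets the systolic change criterion at ">25% mmHg Increased or decreased from Baseline". Protocol section 9.2.3.3 lists "systolic blood pressure increase or decrease from Baseline >25% mmHg, >160 mmHg, or <90 mmHg", and the safety part of the synopsis uses the same words. The BMI row of the SAP table has a single unit: ">10% increased or decreased from Baseline".

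The counting rule in SAP 3.6.3 gives each criterion one numerator. A patient enters it with "at least one post-baseline outlier value within the analysis period" (and a normal baseline for that criterion). The SAP table has one row for systolic change and one for SBP above 160 mmHg. It has no row for SBP below 90 mmHg, although the protocol lists that threshold. SAP section 5 records no changes from the protocol's analyses.

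Outside the threshold table, SAP 3.6.3 states: "Vital signs and change from Baseline in vital signs will be summarized descriptively at each visit by treatment group". It also has all vital-sign measurements listed.

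**The concern.** A threshold cannot be in percent and in mmHg at once. A programmer who goes back to the protocol finds the same wording. The introductory phrase about absolute and relative thresholds does not settle the matter either, because SAP 3.6.4 uses it for a list whose only change criteria are in msec: "QTcF increase from Baseline >30 msec and >60 msec".

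Safety is the trial's secondary objective, and this is the only change-from-baseline blood pressure threshold in the plan. With 12 patients per arm, the choice of unit can move the count in an arm by a few patients.

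The single row raises a second question. If rises and falls share one count, the count does not show which way pressure moved, and a drop in one direction can offset a gain in the other. This matters more because the SAP omits the SBP <90 mmHg criterion: the combined row is then the only threshold in the SAP table that can register a fall.

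**Working it through.** The documents give no outlier rate for this criterion, so there is no figure to reproduce. The check compares the two readings directly.

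**1. Where the readings differ.** The percent cut-off is 0.25 × baseline; the mmHg cut-off is 25. They coincide only at a baseline of 100 mmHg. Protocol section 4.2 excludes "average systolic blood pressure >160 mmHg" at Screening, so baselines up to about 160 are relevant.

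| Baseline (mmHg) | Percent cut-off (mmHg) | mmHg cut-off |
|---|---|---|
| 90 | 22.5 | 25 |
| 100 | 25 | 25 |
| 120 | 30 | 25 |
| 140 | 35 | 25 |
| 160 | 40 | 25 |

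Examples:
- 140 to 170: +30 mmHg, 30/140 = +21.4%. Flagged in mmHg only.
- 160 to 130: −30 mmHg, 30/160 = −18.8%. Flagged in mmHg only.
- 90 to 114: +24 mmHg, 24/90 = +26.7%. Flagged in percent only.

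**2. One record, closed form.** Assume baseline 140, a normally distributed change with SD 15 mmHg, and no drug effect.
- Percent: 2 × [1 − Φ(35/15)] = 2 × 0.98% = 1.96%.
- mmHg: 2 × [1 − Φ(25/15)] = 2 × 4.78% = 9.56%.

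**3. Patients ever flagged.** Protocol Appendix A schedules vital signs after baseline at Visits 3, 4, 5, 7, 9, 10 and 11, so there are up to seven readings. The remaining inputs are assumptions, not document figures: true SBP normal with mean 135 and between-patient SD 12; one baseline reading; within-patient SD 8, 10 or 12; no drug effect. A simulation of this model gives:

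| Within-patient SD | mmHg reading | Percent reading | Ratio |
|---|---|---|---|
| 8 | 13.5% | 2.8% | 4.8 |
| 10 | 32.7% | 10.5% | 3.1 |
| 12 | 52.3% | 22.7% | 2.3 |

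At SD 10, a 12-patient arm would have 12 × 0.327 = 3.9 flagged patients against 12 × 0.105 = 1.3. Visit 4 may be a phone visit without vital signs. With six readings the SD 10 figures are about 30% and 9.6%, a similar ratio.

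**4. Direction.** Same model, percent reading, SD 10, seven readings:

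| True shift | Combined row | Relevant direction alone |
|---|---|---|
| Fall of 8 mmHg | 10.5% to 14.0% (+3.5 points) | falls: 2.6% to 11.6% (+9.0 points) |
| Rise of 8 mmHg | 10.5% to 19.8% (+9.3 points) | rises: 7.9% to 19.4% (+11.5 points) |

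The combined row keeps 3.5/9.0 = 39% of the contrast for a fall and 9.3/11.5 = 81% for a rise. The asymmetry comes from the baseline denominator. A low baseline reading lowers the percent cut-off and tends to be followed by higher readings, so with no drug effect most flags are rises (7.9% against 2.6%). A true fall removes many of those while adding falls. On the mmHg reading, shifts of +8 and −8 give the same combined rate, about 43%.

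**The case against.** The strongest reply is that this is a stray unit. All three places print a percent sign, and the BMI row uses the same form of words in percent, so a sensible programmer would compute a percentage. That makes percent the likelier intent. It does not make it the stated rule, and a threshold used for a table should not depend on inference.

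A reader might infer that the unit could be picked after the results are seen. The documents do not support that. The SAP is to be final before database lock (section 1), the statistical team stays blinded until lock (section 4.1), and separate programming specifications (section 6), not available here, may already fix the unit.

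A reader might also infer that every systolic record is in doubt. It is not: only changes between the two cut-offs are affected.

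On direction, the SAP does not say outright that rises and falls share one count; this follows from the single row and the one-numerator rule. A two-sided screening flag is a legitimate choice, and the BMI row has the same form. By-visit change from Baseline, the row above 160 mmHg and the listings all give directional information, and no test or decision uses this row. These points stand and limit the weight of the finding. They do not remove the case for separate rows while the SAP has no low-SBP threshold.

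**Conclusion.** The point holds as a minor safety-reporting defect. The threshold is ambiguous in all three places, and the documents do not state which unit was meant. The 2.3- to 4.8-fold difference in flagged patients rests on the assumed mean, SDs and number of readings; the existence of the ambiguity does not.

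The combined row cannot show direction. It would be too strong to say that it hides any directional effect: under the assumed model and the percent reading the loss is large for a fall and modest for a rise, and direction stays visible in the by-visit summaries and listings. The primary endpoint is unaffected.

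**What to change.** Before unblinding:

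1. State the systolic change criterion in one unit, and correct SAP 3.6.3 Table 1, protocol section 9.2.3.3 and the synopsis together.
2. Replace the single row with two, one for increases from Baseline and one for decreases, each counted by arm.
3. Reconcile the SAP table with the protocol's SBP <90 mmHg criterion: either add the row, or record and explain the omission in SAP section 5.

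The cost is a wording correction with a matching protocol clarification and an extra table row, plus one more if the low-SBP criterion is restored. No new data are needed.
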